This study procedure will not be performed at this time point for the MenACWY group, administered only 1 dose of vaccine at Visit 1 (no Visit 3 performed)

Blood sample collection will be performed before vaccine(s) administration.

Subjects who receive a single dose of MenACWY only will return their pDiary at Visit 2 (Day 31). All subjects in the other treatment groups will return their first pDiary at Visit 3 (Day 61) and will receive a second pDiary for the remainder of the study.

● is used to indicate a study procedure that requires documentation in the individual eCRF.

○ is used to indicate a study procedure that does not require documentation in the individual eCRF.

AE = adverse event; AESI = adverse event of special interest; eCRF = electronic case report form; GSK = GlaxoSmithKline; Pre-Vacc: pre-vaccination; Post-Vacc: post-vaccination; SAE = serious adverse event

Whenever possible, the investigator should arrange study visits within the interval described in [Table 5](#).

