**Table 5 Intervals between study visits**

Interval	Optimal length of interval	Allowed interval (Min – Max) 
Visit 1 (Day 1) → Safety call 1 (Day 15)	14 days	11 days – 17 days (Days 12 – 18)
Visit 1 (Day 1) → Visit 2 (Day 31)	30 days	23 days – 40 days (Days 24 – 41)
Visit 1 (Day 1) → Visit 3 (Day 61)	60 days	53 days – 70 days (Days 54 – 71)
Visit 3 (Day 61) → Safety call 2 (Day 75)	14 days	11 days – 17 days (Days 72 – 78)
Visit 3 (Day 61) → Visit 4 (Day 91)	30 days	23 days – 40 days (Days 84 – 101)

Safety call time intervals will not be used for the assessment of protocol deviations. The Study Day ranges shown in the table are based on optimal intervals; the actual Study Day ranges for Safety Call 2 and Visit 4 will be based on when Visit 3 occurs.

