### **8.3. Detecting and recording adverse events, serious adverse events, and pregnancies**

#### **8.3.1. Time period for detecting and recording adverse events, serious adverse events, and pregnancies**

The time period for collecting and recording AEs will begin at the time of informed consent signature and through study discharge.

All AEs starting within 30 days following administration of each dose of study vaccine(s) must be recorded into the subject records and the appropriate section of the eCRF, irrespective of intensity or whether or not they are considered vaccination-related.

The time period for collecting and recording SAEs will begin at the time of informed consent signature and will end 30 days following administration of the last dose of study vaccine(s) for each subject. See Section [8.4](#) for instructions on reporting of SAEs.

All medically attended AEs will be collected and recorded from the time of informed consent signature.

All AEs/SAEs leading to withdrawal from the study will be collected and recorded from the time of informed consent signature.

In addition to the above-mentioned reporting requirements and in order to fulfil international reporting obligations, SAEs that are related to study participation (i.e. protocol-mandated procedures, invasive tests, a change from existing therapy) or are related to a concurrent GSK medication/vaccine will be collected and recorded from the time the subject consents to participate in the study until she/he is discharged from the study.

The time period for collecting and recording pregnancies will begin at the time of informed consent signature and will end 30 days following administration of the last dose of study vaccine(s). See Section [8.4](#) for instructions on reporting of pregnancies.

The time period for collecting and recording of AESIs will begin at the time of informed consent signature and will end 30 days following administration of the last dose of study vaccine(s). See Section [8.4](#) for instructions on reporting of AESIs.

An overview of the protocol-required reporting periods for AEs, SAEs, and pregnancies is given in [Table 11](#).

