### **10.9.3. Analysis of other adverse events**

#### Unsolicited Adverse Events

This analysis applies to all AEs occurring during the study, judged either as probably related, possibly related, or not related to vaccination by the investigator, recorded in the Adverse Events eCRF, with a start date on or after the date of first vaccination. Adverse events starting prior to the first vaccination will only be listed. The original verbatim terms used by investigators to identify AEs in the eCRFs will be mapped to preferred terms using the MedDRA dictionary. The AEs will then be grouped by MedDRA preferred terms into frequency tables according to system organ class.

All reported AEs, as well as AEs judged by the investigator as at least possibly related to study vaccine(s), will be summarized according to system organ class and preferred term within system organ class. These summaries will be presented by study group and by interval of study observation. When an AE occurs more than once for a subject, the maximal severity and strongest relationship to the study group will be counted.

Separate summaries will be produced for the following categories:

- SAEs
- AEs that are possibly or probably related to vaccine(s)
- AEs leading to withdrawal
- AEs leading to a medically attended visit
- AESI

Data listings of all AEs will be provided by subject. In addition, AEs in the categories above will be provided as listed data.

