Unsolicited AEs will be recorded for 30 days following administration of study vaccine. AEs will be recorded starting from informed consent date if a separate visit occurs before Visit 1 (maximum 5 days before first dose of study vaccine). Serious adverse events (SAEs), medically attended AEs, AEs/SAEs leading to withdrawal, SAEs related to study participation or concurrent GSK medication/vaccines and adverse events of special interest (AESIs) will be recorded from the date of informed consent through Visit 4 (MenACWY group will have AEs recorded through Visit 2). Subjects will receive a safety follow-up call 14 days (or within 11 days - 17 days) after each visit where study vaccine is administered. Solicited AEs will be recorded in subject diaries by the subject/subject's parent(s)/LAR(s) for 7 days after the vaccine is administered (including the day on which the vaccine is administered).

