### Missing Data

For safety analyses, subjects who missed reporting symptoms (solicited or unsolicited) or concomitant medications will be analyzed to determine the missing mechanism. For the analysis of solicited symptoms, implausible measurements will not be replaced but they will be excluded from the analyses. Missing values will not be imputed for solicited/unsolicited AEs or concomitant medications.

In order to minimize the effect of missing data, the study period will be divided into time intervals for the safety analyses. For unsolicited AEs, the study period will be divided into the following intervals: all unsolicited AEs reported from day 1 to day 31 after vaccination (day of vaccination = day 1, Visit 1 and Visit 3 will be assessed separately and combined), medically attended AEs reported during the entire study period, AEs leading to premature withdrawal from the study during the entire study period, SAEs reported during the entire study period and AESI reported during the study period for the Unsolicited Safety Set.

Concomitant medications will be assessed for the entire study period for the Overall Safety Set.

Solicited AE data will be analyzed by the following intervals: 30 minutes post-vaccination on day of vaccination, 1 – 3 days post-vaccination (including the day of vaccination as day 1, excluding 30 minutes post-vaccination), 4 days – 7 days post-vaccination, and 1 day - 7 days (including the day of vaccination as day 1, excluding 30 minutes post-vaccination). Intervals will be assessed for Visit 1 and Visit 3, separately and combined, for the Solicited Safety Set. Solicited local AEs will be considered separately by vaccine for study groups where two vaccinations are administered at each visit, and also separately by location

A subject will be classified as having missing data within the specified intervals as described below:

- Solicited AEs
  - Temperature will be regarded as missing if “Temperature taken” = “No” at every time point within the interval (on Post-vaccination Body Temperature eCRF page).
  - Pain will be regarded as missing if no intensity values are recorded for Vaccine A and Vaccine B separately at every time point within the interval (on Vaccine A/Vaccine B Solicited Local Adverse Event eCRF pages). An intensity value of ‘None’ is a valid value and will not be considered a missing value.

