### 7.2.2 Visit Attendance

The number and percentage of subjects who attended a visit or received a safety call within the interval described in Table 1 will be presented for the following visits:

- Visit 1
- Safety Call 1
- Visit 2
- Visit 3 (excluding the MenACWY group)
- Safety Call 2 (excluding the MenACWY group)
- Visit 4 (excluding the MenACWY group)

The number and percentage of subjects who received a 3 day pDiary reminder call and a 5 day pDiary reminder call after each visit, and if the subject/legal guardian was reached, will also be included.

Listings will be provided for the All Enrolled Set to provide details of visit attendance, safety calls, blood samples and pDiary reminder calls.

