### **9.1.2 Unsolicited Adverse Events**

An unsolicited AE is an AE that was not solicited using a pDiary and that was spontaneously communicated by a subject/parent(s)/LAR(s) who has signed the informed consent or a solicited local or systemic that meets the criteria described in Section 9.1.1. Solicited AEs lasting more than 7 days after vaccination (including the day of vaccination) are also recorded as AEs.

The original verbatim terms used by investigators to identify AEs in the Adverse Events page of the eCRF will be mapped to preferred terms (PT) using MedDRA version 20.1 or higher. The AEs will then be grouped by MedDRA preferred terms according to system organ class (SOC).

Unsolicited AE summaries will be based on the Unsolicited Safety Set.

The following summaries will present the number and percentage of subjects reporting each AE and will be presented by SOC and PT for each study group, grouped by three time points: 30 days post-vaccination at any visit, 30 days post-vaccination at Visit 1 and 30 days post vaccination at Visit 3. Note that the MenACWY group will not be included in the 30 days post vaccination at Visit 3 summary):

- Any unsolicited AE
- Unsolicited AEs that are possibly or probably related to vaccine(s) - (Relationship to study treatment = Yes)
- Severity of unsolicited AE

Additional summaries will present the number and percentage of subjects reporting AEs in the following categories and will be presented by SOC and PT for each study group from Day1 through till end of study for the Overall Safety Set:

- AEs leading to withdrawal from the study
- AEs leading to withdrawal from the study vaccine
- AEs leading to a medically attended visit
- AEs leading to death
- SAEs
- SAEs that are possibly or probably related to vaccine(s)
- SAEs leading to death
- SAEs that are possibly or probably related to vaccines(s) and leading to death

Listings will be presented for Any AEs, AEs that are possibly or probably related to vaccine(s), AEs leading to withdrawal from the study, AEs leading to withdrawal from the study vaccine, AEs leading to medically attended visit, AEs leading to death, SAEs, SAEs that are possibly or probably related to vaccine(s), SAEs leading to death, SAEs that are possibly or probably related to vaccine(s)

and leading to death. AEs that were reported as occurring prior to a subject receiving any study vaccine will only be included on the Any AEs listing.

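### SAEs, medically attended AEs, AEs leading to study withdrawal and AESIs are tabulated only over the whole study, although MenACWY follow-up is nominally 31 days against 91 in the other groups

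*SAP*

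**What the plan says.** **Tables.** SAP 9.1.2 gives the number and percentage of subjects with SAEs, medically attended AEs and AEs leading to study withdrawal, "presented by SOC and PT for each study group from Day1 through till end of study for the Overall Safety Set". SAP 9.1.3 gives the same statistic for AESIs, in each group, from consent to Day 91. SAP 4.3 (Missing Data) divides the study into intervals for the safety analyses but leaves these categories whole: "AEs leading to premature withdrawal from the study during the entire study period, SAEs reported during the entire study period", and likewise for medically attended AEs and AESIs.

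**Follow-up.** SAP 3.1 runs these categories to Visit 4, with the exception that the "MenACWY group will have AEs recorded through Visit 2". Protocol 8.3.1 says that SAE collection "will end 30 days following administration of the last dose of study vaccine(s) for each subject", and sets the same limit for AESIs. Footnote 4 to protocol Table 4 describes the MenACWY group as "administered only 1 dose of vaccine at Visit 1 (no Visit 3 performed"). SAP 7.2.2 leaves that group out of attendance at Visit 3, Safety Call 2 and Visit 4.

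**Endpoint text.** The safety endpoints in the protocol synopsis, protocol 10.2 and SAP 3.2.2 place these categories in all study groups from consent to Visit 4 (Day 91). The neighbouring solicited and unsolicited AE bullets carry a MenACWY exception; this one does not.

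**The concern.** A table of percentages by group invites reading across the columns. If MenACWY is observed to Visit 2 and the others to Visit 4, the gap between a two-dose group and MenACWY mixes three things: longer observation, a possible effect of the second dose, and any vaccine difference. Nothing in the planned table separates them. No common window, person-time rate or follow-up footnote is specified, and the Day 91 label tells the reader that follow-up was equal.

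The SAP already has the remedy. In 9.1.2, any unsolicited AE, related unsolicited AEs and severity are shown for the 30 days after Visit 1, the 30 days after Visit 3, and both together, with MenACWY left out of the Visit 3 window. The four categories at issue get no such split.

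The conflict over the end point also matters in itself. As written, sites and programmers cannot tell whether an absence of MenACWY events after Day 31 means that none occurred or that none were sought.

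**Working it through.** **1. The plan's own safety figure.** Protocol 10.4 and SAP 4.1 give a 99.3% probability of detecting an AE that occurs in 1 of 100, with 500 subjects. Check: 1 − 0.99^500 = 0.9934, which agrees. The figure gives every subject the same chance of showing the event. If the 1% is read as a Day 91 risk and MenACWY contributes 31/91 of the observation, it becomes 1 − 0.99^(400 + 100 × 31/91) = 0.987. The trial-wide figure hardly moves; the issue is the comparison between columns.

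**2. Where MenACWY collection ends, by category.**

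- SAEs and AESIs: Day 31 under protocol 8.3.1 (30 days after a single dose on Day 1), and Visit 2 under SAP 3.1. These agree.
- Medically attended AEs and AEs leading to study withdrawal: protocol 8.3.1 gives a specific start (consent) but no category-specific end. The Day 31 end rests on SAP 3.1 and on the absence of later MenACWY visits.
- All four: Day 91 in the endpoint text, and in SAP 9.1.3 for AESIs.

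**3. Nominal ratio.** 91/31 = 2.9. The part of two-dose follow-up with no MenACWY counterpart is (91 − 31)/91 = 66%.

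**4. Range for SAEs and AESIs.** Protocol Table 5 allows Visit 3 on Days 54 to 71. Adding 30 days, collection in the two-dose groups ends between 54 + 30 = Day 84 and 71 + 30 = Day 101. Against Day 31 the ratio runs from 84/31 = 2.7 to 101/31 = 3.3.

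**5. Effect on a crude percentage.** The documents give no event rates for these categories, so the 31-day risks p below are assumptions. With the same constant hazard in every group, and hence no vaccine or second-dose effect, the Day 91 risk is 1 − (1 − p)^(91/31):

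| Assumed 31-day risk (MenACWY column) | Day 91 risk (two-dose column) | Ratio |
|---|---|---|
| 1% | 2.9% | 2.9 |
| 5% | 14.0% | 2.8 |
| 10% | 26.6% | 2.7 |

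At 1%, with about 100 per group, this is roughly one subject against three, which chance alone could easily produce. At 5% or 10%, which could be relevant to medically attended AEs, it is about 5 against 14 or 10 against 27. In a common window of 30 days after the first dose, the expected ratio under the same assumption is 1.

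**6. Do other planned outputs fill the gap?** Only in part. An event of these kinds that is an unsolicited AE within 30 days of Visit 1 should enter the general table for that window, but it is not labelled there as an SAE, medically attended AE, withdrawal AE or AESI. The further 30-day summary that closes SAP 9.1.2 covers any visit and excludes SAEs. The listings would let a reader count post-dose-1 events by hand.

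**The case against.** The strongest reply is that this is a matter of presentation. One dose against two is an open design feature, protocol 10.10 makes every analysis descriptive, and no safety contrast with MenACWY is planned. The trial's question concerns the combined vaccine against separate administration, and those groups share the same planned follow-up. The general unsolicited table and the listings already hold most of the information. All of this stands, and it limits the point to how a few tables are read. It does not answer the Day 91 label, nor the lack of a comparable percentage for these categories.

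Four stronger readings are tempting, and the documents do not support them:

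- *That the SAP departs from the protocol.* Protocol 10.9.3 says "These summaries will be presented by study group and by interval of study observation", but this refers to the preceding summaries of all AEs and of those at least possibly related, which the SAP does split. The list of separate summaries comes afterwards with no promise of intervals.
- *That the procedure tables show Day 91 follow-up was intended for MenACWY.* The recording rows for these categories lack footnote 4 at the later contacts. But so do the Visit 3 pregnancy test, eligibility check and physical examination, although the footnote itself says that group has no Visit 3. It is applied too unevenly to show intent.
- *That follow-up could differ by a factor of 4.6.* This pairs a Day 24 Visit 2 with a Day 111 Visit 4. SAE and AESI collection is tied to the last dose, which gives 2.7 to 3.3.
- *That the safety comparison of MenABCWY with separate vaccines is biased.* It is not; these groups have the same planned follow-up.

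Protocol Table 11 sets out reporting periods by category, but its cells could not be read in the available text. Its footnote on MenACWY at Visit 3 is attached only to the solicited and unsolicited rows, so it does not settle the matter.

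**Conclusion.** The point holds as a modest one. On SAP 3.1, protocol 8.3.1 and the visit schedule, the planned tables set nominally 31 days of MenACWY follow-up beside 91 days in the two-dose groups, in undivided crude percentages. The endpoint text and SAP 9.1.3 say Day 91 for all or each group and must be reconciled with SAP 3.1 and protocol 8.3.1.

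Confidence is highest in the conflict of wording. The table-layout part depends on Visit 2 being the MenACWY end point; if it is Day 91, that part falls away. The size in percentages depends on assumed event rates and a constant, equal hazard, so it is illustrative. No formal test is affected.

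**What to change.** State one MenACWY collection end point for each category, and use it in the safety endpoint text (protocol synopsis and 10.2, SAP 3.2.2), protocol 8.3.1, SAP 3.1 and SAP 9.1.3. Check protocol Table 11 and the procedure tables against it.

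- **If it is Visit 2, as SAP 3.1 says:** add to the 9.1.2 and 9.1.3 tables a column for the 30 days after Visit 1 in all five groups and a column for the 30 days after Visit 3 in the two-dose groups. Footnote the whole-study column with each group's follow-up. The cost is wording and a few table columns from data already collected. If the intervals are also added to SAP 4.3, its missing-data algorithm and Fisher's exact tests would apply to each of them.
- **If it is Day 91:** SAP 3.1 and protocol 8.3.1 need correcting, and the MenACWY schedule needs the contacts that it now lacks. That is not cheap, but the extra columns would then not be needed for this reason.

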#### **9.1.3 Adverse Events of Special Interest**

Arthritis is the only AESI in this study. Arthritis is defined in section 8.1.6.1 of the protocol. The list of preferred terms corresponding to the diagnosis of arthritis are those included in the MedDRA Standardized MedDRA Queries Narrow “Arthritis”. For any new diagnosis of arthritis in a subject, the investigator must complete an ad-hoc eCRF page on arthritis to characterize the AESI.

The number and percentage of subjects identified as having an AESI will be presented by SOC and PT for each study group from date of informed consent through to Day 91. AESI will be presented for the Overall Safety Set.

A listing will be provided for subjects identified as having an AESI.

Missing data will be handled as described in Section 4.3.

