**Table 1 Visit Intervals**

Interval	Optimal length of interval	Allowed interval (Min – Max) 
Visit 1 (Day 1) → Safety call 1 (Day 15)	14 days	11 days – 17 days (Days 12 – 18)
Visit 1 (Day 1) → Visit 2 (Day 31)	30 days	23 days – 40 days (Days 24 – 41)
Visit 1 (Day 1) → Visit 3 (Day 61)	60 days	53 days – 70 days (Days 54 – 71)
Visit 3 (Day 61) → Safety call 2 (Day 75)	14 days	11 days – 17 days (Days 72 – 78)

Visit 3 (Day 61) → Visit 4 (Day 91)	30 days	23 days – 40 days (Days 84 – 101)
-------------------------------------	---------	-----------------------------------

Safety call time intervals will not be used for the assessment of protocol deviations. The Study Day ranges shown in the table are based on optimal intervals; the actual Study Day ranges for Safety Call 2 and Visit 4 will be based on when Visit 3 occurs.

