**Table 3 Serogroup Display Order**

Serogroup (strain)	Display Order
Serogroup B (M14459)	1
Serogroup B (M07-0241084)	2
Serogroup B (96217)	3
Serogroup B (NZ98/254)	4
Serogroup C	5
Serogroup Y	6
Serogroup W-135	7
Serogroup A	8

Baseline will be defined as the value recorded at Visit 1. The study day will be calculated as assessment date - first dose date of study vaccine + 1 if the study date is on or after first dose date of study vaccine, or assessment date – first dose date of study vaccine if the study date is prior to the first dose date of study vaccine.

Throughout the study, logarithmic transformations and anti-logarithms will use base 10.

Statistical analysis will be performed using SAS® Version 9.3 or higher. Standardized and validated SAS macros from PPD will be used to set up table, listing, figure (TLF) formats (headers/footers and tabulation format) and tabulate the summaries. All tables and listings will be independently validated using double programming; datasets behind the figures will be independently validated using double programming and figure outputs will be independently validated manually.

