### 9.1 Adverse Events

Solicited AEs, unsolicited AEs, SAEs, medically attended AEs, AEs leading to withdrawal from treatment or from the study, and AEs of special interest (AESI) that occur post-vaccination will be summarized and also presented in listings. AEs occurring prior to a subject receiving any study vaccine will be listed only.

The definitions for SAEs and medically attended AEs and AESIs can be found in protocol sections 8.1.2 and 8.3.3.4 respectively. Further information about AESIs can be found in Section 9.1.3.

Incomplete onset dates and end dates for any AEs will be imputed to determine if the event occurred within the time period specified for AE summaries as described in sections 9.1.1, 9.1.2 and 9.1.3. Actual dates recorded will be presented in listings, imputed dates will not be presented. Incomplete dates will be imputed as follows:

Missing onset dates (where UK and UKN indicate unknown or missing day and month respectively):

- UK-MMM-YYYY: If the month and year are different from the month and year of the first dose of study vaccine, assume 01-MMM-YYYY. If the month and year are the same as the first dose of study vaccine month and year, and the end date (after any imputation) is on or after the first dose of study vaccine, then assume the date of the first dose of study vaccine. If the month and year are the same as the first dose of study vaccine month, and year and the end date (after any imputation) is prior to the first dose of study vaccine, then assume the end date for the onset date.
- DD-UKN-YYYY/UK-UKN-YYYY: If the year is before the year of first dose of study vaccine, assume DD-JAN-YYYY/01-JAN-YYYY of the collected year. If the year is after the first dose and the same as the second

dose, assume DD-JAN-YYYY/01-JAN-YYYY. If the year is the same as the first dose of study vaccine year, and the end date (after any imputation) is on or after the first dose of study vaccine, then assume the date of the first dose of study vaccine. If the year is the same as the first dose of study vaccine, and the end date (after any imputation) is prior to the first dose of study vaccine, then assume the end date for the onset date.

Missing end dates (where UK and UKN indicate unknown or missing day and month respectively):

- UK-MMM-YYYY: Assume the last day of the month.
- DD-UKN-YYYY: Assume DD-DEC-YYYY.
- UK-UKN-YYYY: Assume 31-DEC-YYYY.

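### The AESI table in SAP 9.1.3 starts at consent, against the SAP's own post-vaccination rule, and ends at a Day 91 that is not reconciled with Visit 4 or with 30 days after the last dose

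*SAP*

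**What the plan says.** **The AESI table.** SAP 9.1.3 orders the number and percentage of subjects with an AESI, for the Overall Safety Set, and says that they "will be presented by SOC and PT for each study group from date of informed consent through to Day 91". It adds: "A listing will be provided for subjects identified as having an AESI". No day limit is given for that listing.

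**Events before vaccination.** SAP 9.1 lists the kinds of event that it covers, "and AEs of special interest (AESI) that occur post-vaccination will be summarized and also presented in listings", and then states: "AEs occurring prior to a subject receiving any study vaccine will be listed only". SAP 9.1.2 confines pre-vaccination events to the listing of all AEs. Protocol 10.9.3 has the same rule: "Adverse events starting prior to the first vaccination will only be listed".

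**End of AESI follow-up.** Three descriptions stand beside the one in 9.1.3:
- SAP 3.1: "adverse events of special interest (AESIs) will be recorded from the date of informed consent through Visit 4", with AE recording through Visit 2 for the MenACWY group.
- SAP 3.2.2: the endpoint runs from consent to Visit 4, with Day 91 in brackets as the label of that visit.
- Protocol 8.3.1: AESI collection ends 30 days after the last dose.

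**Study day.** SAP section 4 (below Table 3) says: "The study day will be calculated as assessment date - first dose date of study vaccine + 1" for dates on or after the first dose. The footnote to SAP Table 1 says that "the actual Study Day ranges for Safety Call 2 and Visit 4 will be based on when Visit 3 occurs".

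**The concern.** The AESI-specific section and the general AE section of the same SAP give different rules for when an arthritis case enters a by-group table. The neighbouring tables in SAP 9.1.2 (SAEs, withdrawals, medically attended events) start at Day 1, so the consent start is peculiar to the AESI table. The SAP requires independent double programming of tables, and two programmers could each follow a defensible sentence and produce different AESI counts.

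The closing day raises a second question. A fixed day does not move with the second dose, whereas Visit 4 and the 30-day period after the last dose both do.

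Arthritis is the only AESI, and Protocol 1.3.1 bases it on a signal observed for rMenB+OMV NZ. With about 100 subjects per group, one case included or left out moves a group's percentage by about 1 point (1/100). The study is open-label, so a window chosen after cases are known would be hard to defend.

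**Working it through.** **Start of the window (comparison of text)**

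1. Consent can be taken at a separate visit up to 5 days before Visit 1 (footnote 1 to the schedule of procedures in both documents), and AESIs are recorded from consent (SAP 3.1, Protocol 8.3.1). An AESI record with onset before dose 1 can therefore exist.
2. SAP 9.1.3 read literally puts that record in the by-group table. SAP 9.1, SAP 9.1.2 and Protocol 10.9.3 keep it out and send it to a listing.
3. The Overall Safety Set does not settle the matter. It selects vaccinated subjects and does not filter events by onset date.

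The two rules cannot both be followed for such a record. The period at issue is at most 5 days per subject.

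**End of the window (day arithmetic)**

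Inputs from SAP Table 1: the second dose (Visit 3) is allowed on Days 54 to 71, and Visit 4 is allowed 23 to 40 days after Visit 3. From Protocol 8.3.1: collection ends 30 days after the last dose.

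Reproducing the plan's figure first: with Visit 3 on its optimal Day 61, Visit 4 may fall from 61 + 23 = Day 84 to 61 + 40 = Day 101. This matches the Days 84 to 101 in SAP Table 1.

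Now let the second dose fall on day *d*. The 30-day period ends on day *d* + 30, and the latest in-window Visit 4 is on day *d* + 40. If Day 91 is the calculated study day, the days lost are max(0, *d* + 30 − 91) against the 30-day rule and max(0, *d* + 40 − 91) against the Visit 4 rule.

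| Dose 2 day | 30-day period ends | Days lost of 30 | Latest Visit 4 | Most days lost up to Visit 4 |
|---|---|---|---|---|
| 54 | 84 | 0 | 94 | 3 |
| 61 | 91 | 0 | 101 | 10 |
| 62 | 92 | 1 | 102 | 11 |
| 66 | 96 | 5 | 106 | 15 |
| 71 | 101 | 10 | 111 | 20 |

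On this reading, any in-window second dose on Days 62 to 71 loses 1 to 10 of its 30 post-dose days. In the last row, 10 of the 20 days (Days 102 to 111) lie after the end of collection in Protocol 8.3.1, so they count only if follow-up runs to Visit 4 as SAP 3.1 says.

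If Day 91 means Visit 4, nothing up to Visit 4 is lost.

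For MenACWY, SAP 3.1 ends AE recording at Visit 2 (Days 24 to 41), so neither reading of Day 91 describes that group's follow-up.

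**The case against.** The best case for the plan has four parts.

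- **Day 91 is a visit label.** The documents use it for Visit 4 or the last visit. The endpoint in SAP 3.2.2 does so. The period for concomitant vaccinations, which Protocol 6.7.1 ends at Day 91, is restated in SAP 7.1.2 as ending at the last study visit. This stands, and it makes the visit reading plausible, perhaps the likelier one. It does not settle 9.1.3, where the visit is not named and the only defined study day counts from dose 1.
- **SAP 9.1 already covers AESIs by name.** A reader might infer from 9.1.3 that pre-vaccination arthritis will be attributed to a study group. The documents do not establish that, because 9.1 forbids it, and Protocol 8.1.1 sends conditions present before the first vaccination to medical history. What stands is a contradiction, which the specific section could win when the table is programmed.
- **Late events are not hidden.** The AESI listing has no day limit. Arthritis within 30 days after dose 2 also falls in the by-group table of unsolicited AEs after Visit 3 (SAP 9.1.2), and serious arthritis falls in the SAE table, which runs to the end of the study. This stands. Only the AESI counts and percentages are at risk.
- **The effect is small.** The separate consent visit is optional, all analyses are descriptive (Protocol 10.10), and no arthritis rate is given. This also stands.

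**Conclusion.** The point holds as an inconsistency in the SAP that should be corrected.

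The start of the AESI window in 9.1.3 contradicts SAP 9.1, SAP 9.1.2 and Protocol 10.9.3. The period affected is at most 5 days before dose 1.

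The end is unreconciled. Whether anything is lost depends on an assumption that the documents do not settle: none up to Visit 4 if Day 91 means that visit, or 1 to 10 of the 30 post-dose days for second doses on Days 62 to 71 if it is the calculated study day.

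A reader might go further and infer that late arthritis is certainly cut off, or that up to 20 days of collected data are ignored. The documents do not support the first, because Day 91 is elsewhere the label of Visit 4. The second needs the study-day reading together with a follow-up that runs to the latest allowed Visit 4, against the 30-day collection period in Protocol 8.3.1.

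Few events are likely to be affected. No expected number can be computed, because the documents give neither an arthritis rate nor the spread of second-dose dates.

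**What to change.** - **In SAP 9.1.3**, replace the window with: AESIs with onset on or after the first study vaccination, through the end of each subject's AESI collection period as actually dated. Drop the fixed Day 91. AESIs with earlier onset are listed only; name the listing, since SAP 9.1.2 restricts such events to the listing of all AEs.
- **State the end of AESI collection once**, reconciling Visit 4 (Visit 2 for MenACWY) in SAP 3.1 with the 30 days after the last dose in Protocol 8.3.1, and refer to that statement from 9.1.3.
- **In SAP 3.2.2**, note that the consent start is the collection window and does not define what is summarised by group.

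The cost is one sentence in SAP 9.1.3 and a short reconciliation elsewhere in the SAP. No new data are needed. The change should be made before any AESI table is produced.
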